6.4. Covariates and Subgroups

The protocol does not define any formal subgroup analyses, and the study is not adequately powered to perform subgroup analyses. However, immunogenicity analyses will be summarized by age group (18-55 years old and 56+ years old).

6.5. Missing Data and Censoring

There will be no imputations planned for missing data. A complete-case analysis approach will be used, and summaries will be reported for participants with non-missing values only.

For binding antibody and FRNT endpoints, values below the lower limit of quantification (LLOQ) will be kept as reported by the corresponding laboratory if actual numerical values are provided. If actual values below the LLOQ are not provided, the observations will be replaced with a value equivalent LLOQ/2. Values that are greater than the upper limit of quantification (ULOQ) will be kept when actual values are reported from the corresponding laboratory. If actual values above the ULOQ are not provided, observations will be replaced with a value equivalent to the ULOQ.

For live-neutralization endpoint, any values below the lower limit of detection (LLOD) will be assigned a value equivalent to one-half the lower limit of detection for analysis purposes, and any values reported as greater than or equal to the upper limit of detection (and no absolute value is available) will be assigned a value equivalent to the upper limit of detection value. Levels that are reported as above the LLOD but below the LLOQ will be kept as reported by the corresponding laboratory if actual numerical values are provided. If a value is reported to be between the LLOD and LLOQ, but the value was not provided, the observations will be replaced with a value equivalent to the midpoint between LLOD and LLOQ (i.e., [LLOD +LLOQ]/2). If actual values below the LLOQ are not provided, the observations will be replaced with a value equivalent to LLOQ will be kept when actual values are reported from the corresponding laboratory. If actual values above the ULOQ are not provided, observations will be replaced with a value equivalent to the ULOQ.

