3.2. Study Definitions and Derived Variables

For individual participants, the fold rise in immunogenicity endpoints (such as Binding Antibody concentration or Antibody Neutralization Titers) will be calculated by dividing levels observed at post-vaccination visits by levels observed at pre-vaccination, as obtained at Day 1 prior to dose administration.

Also related to immunogenicity endpoints, participants achieving a 4-Fold rise at post-vaccination timepoints/visits are defined as those for whom a 4-fold or higher increase in antibody levels from baseline are observed.

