8. IMMUNOGENICITY EVALUATION

8.1. Primary Immunogenicity Analysis

Summaries and analysis of immunogenicity data will be presented for the mITT population. If there are protocol deviations which may affect the analysis, a per-protocol (PP) analysis may also be performed. See Section 9 for the planned analyses of the co-primary endpoint related to safety.

Serum antibody binding will be measured by two types of Electrochemiluminescence Immunoassay (ECLIA) formats. The first is a 4-plex assay that reports arbitrary units/mL (AU/mL). Results from the 4-plex assay for S-2P-Wa-1 will also be reported in Binding Antibody Units/mL (BAU/mL) as bridged to the WHO International Reference Standard. Conversion from AU/mL to BAU/mL units will be done using conversion factor of 0.0090 for the S-2P-WA-1 variant. Second, a 10-plex assay is a fit for purpose assay that reports area under the curve (AUC) and is used to rapidly assess antibody binding targeting specific variants of concern. Antigens presented in the CSR are S-2P-Wa-1,S-2P-B.1.351, and RDB-B.1.351 for the 4-plex ECLIA and S-2P-Wa-1, S-2P-B.1.617.2, and S-2P-B.1.351 and S-2P-B.1.1.529 for the 10-plex ECLIA (AUC).

Geometric mean (GM), geometric mean fold rise (GMFR) and 4-fold rise rates of SARS-CoV-2 specific antibody binding levels will be calculated at Study Days 1 (GM only), 15, 29, 91, 181, 273, and 366 by study group and will include both tabular and graphical summaries. Note that only timepoints with available results will be reported. Number of participants with non-missing data (n), range, minimum, maximum, GM, GMFR, and 4-fold rise rates will be presented. Corresponding 95% confidence interval (CI) estimates will be presented for GM, GMFR, and 4-fold rise (using Student's t-distribution for GM and GMFR and the Clopper-Pearson binomial method for 4-fold rise rate) at each post vaccination timepoint by study group and age group (starting with Table 13 ending with Table 28). Graphical displays will include boxplots showing the distribution of responses over time by study group (starting with Figure 2 ending with Figure 17) and by study group and age group (starting with Figure 34 ending with Figure 49).

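### Where the laboratory reports only that a value exceeds the ULOQ, SAP 6.5 enters the ULOQ as if it were measured: this lowers the GM, pulls GMFR towards 1 and blocks 4-fold responses, and the tables do not show how often

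*SAP*

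**What the plan says.** SAP 6.5 (Missing Data and Censoring) has two steps for high values. The first retains what the laboratory supplies: "Values that are greater than the upper limit of quantification (ULOQ) will be kept when actual values are reported from the corresponding laboratory". The second covers the case with no number: "If actual values above the ULOQ are not provided, observations will be replaced with a value equivalent to the ULOQ". These rules appear in the paragraph on binding antibody and FRNT and again in the live-neutralization paragraph. That second paragraph also assigns the upper limit of detection when no absolute value exists. Neither paragraph names the pseudovirus assay (PsVNA, Tables 29–36).

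SAP 3.2 defines 4-fold responders as those "for whom a 4-fold or higher increase in antibody levels from baseline are observed". SAP 8.1 then says: "Corresponding 95% confidence interval (CI) estimates will be presented for GM, GMFR, and 4-fold rise". The intervals are Student's t on the log scale for GM and GMFR and Clopper-Pearson for the 4-fold rate, at visits from Day 15 to Day 366. The shells for Tables 13–44 print n, range, GM, GMFR, the 4-fold rate and, for variant neutralization, GMR. None has a row for values at the ULOQ, and no censored-data sensitivity analysis is planned.

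**The concern.** A result reported only as above the ULOQ is a right-censored observation. Entering the limit as a measured value removes the upper tail, which moves the mean and shrinks the SD, so the interval is both misplaced and too narrow. The 4-fold rule gains a hard ceiling, since no post-boost value can be analysed as higher than the ULOQ.

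These summaries carry the co-primary immunogenicity objective, and SAP 6.6 foresees early reports going to public health officials. Participants were vaccinated before Day 1, so baselines are not near zero. Groups 4E, 5E and 6E differ in priming vaccine. If the groups reach the ceiling to different degrees, the differences that the tables display are compressed, and the tables alone would not show it.

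**Working it through.** **Plan's own figure.** SAP Table 4 uses GMT × exp(± t(0.975, n−1) × SD/√n). For GMT 1000, N=50, SD 1.0: 2.0096 × 1.0/√50 = 0.2842, giving (752.6, 1328.7), as printed. With SD 0.5 it gives (867.5, 1152.7), also as printed.

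**Inputs.** From the documents: SD of the log titre 0.5 and 1.0 (SAP Table 4), 50 per group and 25 per age stratum (SAP 4.1), the substitution rule (6.5), the 4-fold definition (3.2). Assumed, because the documents are silent: a normal log titre and the share f above the ULOQ.

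**GM.** Let the ULOQ lie c SDs above the mean log titre, so f = 1 − Φ(c). Capping shifts the mean log titre by −SD × k, with k = φ(c) − c × f. The reported GM divided by the true GM is exp(−SD × k). For f = 20%: c = 0.842, k = 0.280 − 0.842 × 0.20 = 0.112, and exp(−0.5 × 0.112) = 0.946. Coverage is from 100,000 simulated samples per case.

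| Share above ULOQ | k | GM ratio, SD 0.5 | GM ratio, SD 1.0 | Coverage, N=50 | Coverage, N=25 |
|---|---|---|---|---|---|
| 5% | 0.021 | 0.990 | 0.979 | 95% | 95% |
| 10% | 0.047 | 0.977 | 0.954 | 94% | 95% |
| 20% | 0.112 | 0.946 | 0.894 | 87% | 92% |
| 30% | 0.190 | 0.909 | 0.827 | about 60% | 82% |

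In standard errors the shift is k × √N, whatever the SD. At N=50 it is 0.79 with 20% capped and 1.35 with 30%. Smaller cells keep better coverage only because their intervals are wider; the bias is the same.

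**GMFR.** With a ULOQ of 1000, a rise from 260 to 2000 (7.7-fold) is analysed as 3.85. A fall from 2000 to 500 (0.25-fold) is analysed as 0.50. The pull is therefore towards 1: down where titres have risen, up where a capped baseline has waned. With both visits capped at the same ULOQ and an assumed pre/post correlation of 0.6, a true GMFR of 4 is reported as 3.90 (SD 0.5) or 3.82 (SD 1.0) when 10% of post-boost values exceed the ULOQ, and as 3.64 or 3.34 when 30% do.

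**4-fold rate.** If the baseline is at or below ULOQ/4, a capped post value still gives a ratio of at least 4, so no true responder is lost. If the baseline is above ULOQ/4, the ratio stays below 4 and every true responder is lost. When the rise is independent of baseline, reported rate = true rate × P(baseline ≤ ULOQ/4).

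Assume a 5-fold mean rise, SD of the log rise 0.7 and baseline SD 1.0. The true rate is 1 − Φ((ln 4 − ln 5)/0.7) = 0.625, or 63%. Let the baseline GM be a fraction g of the ULOQ:

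| g | P(baseline ≤ ULOQ/4) = Φ(ln(0.25/g)) | Reported rate | Post-boost values above ULOQ |
|---|---|---|---|
| 0.03 | 0.983 | 61% | 6% |
| 0.05 | 0.946 | 59% | 13% |
| 0.135 | 0.731 | 46% | 37% |

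**Right-censored fit.** A normal likelihood that treats the capped values as censored gave about 95% coverage at N=50 on normal data with 20% or 30% above the ULOQ, with the GM within about 1% of the truth.

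**The case against.** The case for leaving the rule alone has four parts.

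*Substitution is only a fallback.* This stands. A reader might infer that every value above the ULOQ is capped, or that no participant with a baseline above ULOQ/4 can ever show a 4-fold rise. Section 6.5 does not support that: a number the laboratory supplies is kept and the rise is counted. The documents do not say that any laboratory withholds such numbers.

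*The size is unknown.* This also stands. The fall from 63% to 46% needs 37% of post-boost values above the ULOQ, and its post-boost log SD is √(1.0² + 0.7²) = 1.22, above the largest SD in SAP Table 4. It is the heavy end of the range and not an expected result.

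*A ceiling would be partly visible.* The shells print the range, the boxplots show distributions, and Listing 9 gives each result. But a maximum equal to the ULOQ does not tell the reader whether one value or fifteen sit there.

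*A censored fit leans on normality.* It does. Breakthrough infections are excluded only from the per-protocol set, so mITT titres may be a mixture. In one check with an assumed 20% shifted component at N=50, the censored fit covered 87% with 20% censored and 74% with 30%, and its GM was 9% and 16% low. That beat substitution but was not nominal. It argues for a sensitivity analysis and against replacing the main estimator.

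That the study is descriptive does not answer the point. A descriptive estimate with a 95% interval should still cover what it describes.

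**Conclusion.** The point holds for results that reach the analysis without a number above the ULOQ. For these the GM is biased down, GMFR is biased towards 1, and a baseline above ULOQ/4 rules out a 4-fold response.

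A reader might go further and say that GMFR is always understated. It is not: the planned visits run to Day 366, and a capped baseline that has waned gives a GMFR that is too high.

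The directions are arithmetic. The size rests on an assumed normal log titre and an assumed share above the ULOQ, so confidence in the size is low. Up to about 10% above the ULOQ the rule costs at most 5% of the GM and leaves coverage at 94–95%; from 20% upwards it matters. The plan neither states that share nor arranges to report it, which makes this a cheap improvement worth making. It does not show that the results are wrong.

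**What to change.** Keep the 6.5 rule for the main tables, and add:

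- **Count.** In the immunogenicity tables, print the number of values set to the ULOQ by group, age stratum and visit.
- **Sensitivity estimate.** Where any value is set to the ULOQ, report GM and GMFR also from a right-censored normal likelihood on the log scale. Treat capped baselines as censored. Dropping them would remove the participants with the highest Day 1 values.
- **4-fold rate.** Report it with the number whose baseline exceeds ULOQ/4, and also restricted to baselines at or below ULOQ/4. Print both: if rises are smaller at higher baselines, the restricted rate will exceed that of the whole group.
- **PsVNA.** State which limit rule applies to it.

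The cost is SAP wording, one table row and one standard routine, with no laboratory work. The sensitivity estimate relies on log-normality and its intervals will usually be wider. Nothing changes where numeric values are supplied.

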6.6. Interim Analyses and Data Monitoring

No formal interim analyses that include sequential testing of a statistical hypothesis will be conducted. Therefore, P-value adjustment will not be made to any analyses.

However, given the need for rapid review and dissemination of study data for formulating public health policies, early reports summarizing safety and immunogenicity endpoints and from data cumulated up to predefined timepoints, may be produced. These reports may be disseminated to public health officials and partners as needed and included in publications and presentations to inform the global scientific community. None of the analyses included in these reports include any formal statistical hypothesis testing; therefore, no adjustment of the significance level will be done.

6.6.1. Safety Monitoring Committee Reports

Given the need for rapid review and dissemination of study data for public health reasons, AEs and SAEs may be reviewed as necessary outside of SMC reviews. The SMC may not need to meet (unless halting rules are met), and materials are provided electronically. Documentation of review and any concerns noted is solicited electronically.

Prior to Protocol Version 4.0, scheduled SMC reviews for Cohort 1 Groups were targeted after participants within a Study Group have completed Day 8. At the time of the writing of Version 1.0 of the SAP, a SMC report after Day 8 had only been produced for Groups 1E, 2E and 3E. From Protocol Version 4.0 onwards, the protocol specifies that the SMC will review separate cumulative AE data reports after all participants within each booster vaccine group of Cohort 1 are dosed and complete Day 29 within Cohort 1.

For Cohort 2 there are no scheduled mandatory reviews by the SMC after participants in this cohort receive the prime, first boost or second boost vaccinations. This is due to the safety database known for EUA vaccines and vaccinations being administered in accordance with CDC guidelines. SMC reviews for Cohort 2 occur if halting rules are triggered, or as requested by the sponsor or PI.

6.6.2. Immunogenicity Review

Data review of immunogenicity endpoints are performed as often as needed to inform public health decisions. These reviews may be performed when participants have completed key immunogenicity visits and the data is available. The analyses are conducted on the mITT analysis set.

Study groups that are concurrently enrolled and planned to receive the same delayed vaccine boost can be included in a single report. The planned summaries and analyses for immunogenicity reports are described in detail in Section 8. The timing of the reports, along with key milestone visits determining the cumulative data to be included in the reports, are informed by the Central Assay Plan and/or determined by DMID.

Data may be disseminated to public health officials and partners as needed and included in publications and presentations to inform the global scientific community.

6.7. Multicenter Studies

Data will be pooled across all clinical sites. Center effects are not anticipated because the sites are using standardized procedures for vaccination and assessment of solicited and unsolicited adverse events, and the study relies on central laboratories for the assessment of immunogenicity endpoints.

6.8. Multiple Comparisons/Multiplicity

The study is not designed to test any specific null hypothesis, and as such no adjustment for multiple comparisons will be performed.

7. STUDY SUBJECTS

7.1. Disposition of Participants

Table 9 will present a summary of the reasons that participants were screened but not enrolled.

The composition of analysis populations, including reasons for participant exclusion, by study group, is presented in Table 8. A listing of participants excluded from analysis populations is also provided in Listing 6.

The disposition of participants in the study will be tabulated by study group (Table 7). The table shows the total number of participants screened, enrolled, received the first/second prime vaccination, received delayed boost dose, terminated from study follow-up, and the number completing the study.

A flowchart showing the disposition of study participants, adapted from the Consolidated Standards of Reporting Trials (CONSORT) Statement [6] will be included (Figure 1). This figure will present the number of participants screened, enrolled, lost to follow-up, and analyzed, by study group.

A listing of participants who discontinued dosing or terminated from study follow-up and the reason will be included in Listing 2.

7.2. Protocol Deviations

A summary of participant-specific protocol deviations will be presented by the reason for the deviation and study group for all participants (Table 5). This table will also include deviations that were collected in the data system as non-participant specific for which a participant ID was provided. A summary of major participant-specific protocol deviations is provided in Table 6. All participant-specific protocol deviations will be included in Appendix 3 as a data listing (Listing 4). All non-participant specific deviations will be presented in Listing 5.

8. IMMUNOGENICITY EVALUATION

8.1. Primary Immunogenicity Analysis

Summaries and analysis of immunogenicity data will be presented for the mITT population. If there are protocol deviations which may affect the analysis, a per-protocol (PP) analysis may also be performed. See Section 9 for the planned analyses of the co-primary endpoint related to safety.

Serum antibody binding will be measured by two types of Electrochemiluminescence Immunoassay (ECLIA) formats. The first is a 4-plex assay that reports arbitrary units/mL (AU/mL). Results from the 4-plex assay for S-2P-Wa-1 will also be reported in Binding Antibody Units/mL (BAU/mL) as bridged to the WHO International Reference Standard. Conversion from AU/mL to BAU/mL units will be done using conversion factor of 0.0090 for the S-2P-WA-1 variant. Second, a 10-plex assay is a fit for purpose assay that reports area under the curve (AUC) and is used to rapidly assess antibody binding targeting specific variants of concern. Antigens presented in the CSR are S-2P-Wa-1,S-2P-B.1.351, and RDB-B.1.351 for the 4-plex ECLIA and S-2P-Wa-1, S-2P-B.1.617.2, and S-2P-B.1.351 and S-2P-B.1.1.529 for the 10-plex ECLIA (AUC).

Geometric mean (GM), geometric mean fold rise (GMFR) and 4-fold rise rates of SARS-CoV-2 specific antibody binding levels will be calculated at Study Days 1 (GM only), 15, 29, 91, 181, 273, and 366 by study group and will include both tabular and graphical summaries. Note that only timepoints with available results will be reported. Number of participants with non-missing data (n), range, minimum, maximum, GM, GMFR, and 4-fold rise rates will be presented. Corresponding 95% confidence interval (CI) estimates will be presented for GM, GMFR, and 4-fold rise (using Student's t-distribution for GM and GMFR and the Clopper-Pearson binomial method for 4-fold rise rate) at each post vaccination timepoint by study group and age group (starting with Table 13 ending with Table 28). Graphical displays will include boxplots showing the distribution of responses over time by study group (starting with Figure 2 ending with Figure 17) and by study group and age group (starting with Figure 34 ending with Figure 49).

Neutralization assays using a validated SARS-CoV-2 pseudovirus neutralization assay (PsVNA) and fit-forpurpose focus reduction neutralization test (FRNT) will be performed using serial dilutions of sera against available variants. Neutralization titers are the serum dilution at which relative luminescence units (RLU; PsVNA) or fluorescent foci (FRNT) are reduced by either 50% (ID₅₀) or 80% (ID₈₀) compared to virus control wells after subtraction of background. Each serum sample will be tested for neutralizing antibodies against each of the pseudoviruses (D614G, B.1.617.2, B.1.351, and B.1.1.529).

ID₅₀ and ID₈₀ will be calculated using methodology such as a 4-parameter non-linear regression model for FRNT and 5-parameter logistic regression model for PsVNA. If multiple results are reported for a sample, a geometric mean of the two results will be used for subsequent analyses. Of one of the reported values for a sample is less than LLOQ, LLOQ/2 will be used in the calculation of the sample geometric mean. ID₅₀ results will be summarized by study group using number of participants with non-missing data, minimum, maximum, range, GM, GMFR, and 4-fold rise rate while ID₈₀ results will be reported in the immunogenicity responses listing only. 95% CI for GM, GMFR, GMR, and 4-fold rise rate will also be presented (using Student's t-distribution for GM, GMFR, GMR and using Clopper Pearson for 4-fold rise rate) at each post vaccination timepoint by study group and age group starting with Table 29 ending with Table 36 for PsVNA and starting with Table 37 ending with Table 44 for FRNT. Graphical displays for PsVNA and FRNT will include boxplots showing the distribution of responses over time by study group (starting with Figure 18 ending with Figure 25 for PsVNA and starting with Figure 26 ending with Figure 33 for FRNT) and by study group and age group (starting with Figure 50 ending with Figure 57 for PsVNA and starting with Figure 58 ending with Figure 65 for FRNT).

Individual immunogenicity responses are shown in Listing 9.

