6.3.2. Modified Intention-to-Treat (mITT) Population

The modified intent-to-treat (mITT) population includes all enrolled participants who received the delayed Janssen- Ad26.COV2.S booster vaccine and contributed both pre- and at least one post-vaccination boost venous blood sample for the corresponding immunogenicity endpoint testing and for which valid results were reported.

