6.3.4. Per Protocol Population

In the final analysis, protocol deviations will be reviewed to determine which protocol deviations may affect the analysis. The per protocol (PP) population will then be defined – and this includes all participants in the mITT subset with the following exclusions:

- Data from all available visits for participants found to be ineligible at enrollment.
- Data from all visits subsequent for the protocol deviations that are considered to affect the science.
- Data from any visit that occurs substantially out of window (i.e., 2x window):
 - Before Day 6 or after Day 10 for Day 8 Visit (Study Visit 2)
 - Before Day 11 or after Day 19 for Day 15 Visit (Study Visit 3)
 - Before Day 25 or after Day 33 for Day 29 Visit (Study Visit 4)
 - Before Day 77 or after Day 105 for Day 91 Visit (Study Visit 5)
 - o Before Day 153 or after Day 209 for Day 181 Visit (Study Visit 6)
 - Before Day 217 or after Day 329 for Day 273 Visit (Study Visit 7)
 - Before Day 310 or after Day 422 for Day 366 Visit (Study Visit 8)

Additional criteria, which do not strictly constitute protocol deviations, will also be applied for exclusion of participants or observations in the PP analysis of immunogenicity endpoints, as follows:

- Receipt of non-study COVID-19 vaccine any time after study vaccination.
- Receipt of seasonal influenza vaccine within 14 days after study vaccination.
- Breakthrough COVID-19 infection either self-reported or Positive N-antibody test.

The live-virus neutralization PP analyses will be based on a subset of 20 participants per study group that were randomly selected, stratified by age for this assay and who meet all criteria of the PP population.

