14.1 Description of Study Participants

14.1.1 Disposition of Participants

Table 7: Participant Disposition by Study Group, All Enrolled Participants

Participant	[Dosed - Boost J	ıp 4E Janssen, anssen] =X)	[Dosed] Boost	up 5E Moderna, Janssen] =X)	[Dosed Boost J	ıp 6E Pfizer, anssen] =X)	All Participants (N=X)		
Disposition	n	%	n	%	n	%	n	%	
Screened							X		
Enrolled	х	100	Х	100	х	100	X	100	
Received delayed boost dose	х	XX	х	XX	x	xx	х	xx	
Early Termination ^a									
[Early term reason 1]									
[Early term reason 2]									
[Early term reason 3]									
Other									
Completed Study									
Note: N=Number of participan ^a Refer to Listing 16.2.1 for rea		pants disconti	nued or termin	nated early.	1	1	1		

Table 8: Analysis Populations by Study Group, All Enrolled Participants

[Implementation note: Other exclusion criteria described in Section 6.3.4 will be added to the per protocol sections of this table when applicable.]

Analysis		[Dosed Boost J	ıp 4E Janssen, [anssen] =X)	[Dosed] Boost	oup 5E Moderna, Janssen] V=X)	Group 6E [Dosed Pfizer, Boost Janssen] (N=X)		All Participants (N=X)	
Populations	Reason Participants Excluded	%	n	%	n			%	n
Safety	Did not receive one dose of the delayed boost vaccine	х	XX	x	XX			х	xx
Modified Intent-	Any Reason								
To-Treat	Did not contribute a pre-vaccination blood sample for which valid immunogenicity results were reported								
	Did not contribute at least one post-vaccination blood sample for which valid immunogenicity results were reported								
Per Protocol,	Any Reason								
Any Timepoint	Found to be ineligible at enrollment ^a								
	Protocol deviation considered to affect the science ^b								
	Visit occurred substantially out of window ^c								
Per Protocol,	Any Reason								
Day 1	Found to be ineligible at enrollment ^a								
	Protocol deviation considered to affect the science ^b								
	Visit occurred substantially out of window ^c								
Per Protocol,	Any Reason								
Day 15	Found to be ineligible at enrollment ^a								
	Protocol deviation considered to affect the science ^b								
	Visit occurred substantially out of window ^c								
Repeat Per Protocol	l rows for Days 29, 91, 181, 273, 366.		•	•	· ·	•		•	
	participants enrolled. pants meeting the criteria. excluded from an analysis population for multiple reasons.								

^a Participant data from all visits are excluded from the per protocol analyses. All instances of exclusion are summarized in this table.

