^b Participant data are excluded from the per protocol analyses at all timepoints that occur at or after this protocol deviation. All instances of exclusion are summarized in this table. Participant data collected up to the time the exclusionary criterion is met is eligible for analysis.

^c Only data from the out of window visit are excluded from the per protocol analyses.

Inclusion/Exclusion Category	Inclusion/Exclusion Criterion	n ^a	⁰∕₀ ^b
Inclusion and Exclusion	Number of participants failing any eligibility criterion	x	100
Inclusion	Any inclusion criterion	x	XX
	[inclusion criterion 1]	x	XX
	[inclusion criterion 2]	x	XX
	[inclusion criterion 3]	x	XX
Exclusion	Any exclusion criterion	x	XX
	[exclusion criterion 1]	x	XX
	[exclusion criterion 2]	x	XX
	[exclusion criterion 3]	x	XX
^a More than one criterion may be r ^b Denominator for percentages is t		-	

Table 9: Ineligibility Summary of Screen Failures

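### Is the per-protocol immunogenicity analysis left optional and undefined, so that late titres mix the study boost with later infection or outside vaccines?

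*SAP*

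**What the plan says.** SAP 8.1, like Protocol 9.4.3, takes mITT as the presentation for immunogenicity and treats PP as conditional: "If there are protocol deviations which may affect the analysis, a per-protocol (PP) analysis may also be performed".

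SAP 6.3.2 admits to mITT anyone boosted who "contributed both pre- and at least one post-vaccination boost venous blood sample for the corresponding immunogenicity endpoint testing", with valid results. SAP 6.5 says of missing values: "A complete-case analysis approach will be used, and summaries will be reported for participants with non-missing values only". Neither section cuts data off at infection or at a vaccine received outside the study. Geometric means, fold rises and 4-fold-rise rates run from Day 15 to Day 366.

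SAP 6.3.4 lists the usual PP exclusions (ineligibility, deviations, out-of-window visits) and then: "Additional criteria, which do not strictly constitute protocol deviations, will also be applied for exclusion of participants or observations in the PP analysis". The three added items are a non-study COVID-19 vaccine at any time after the boost, breakthrough infection by self-report or N-antibody, and "Receipt of seasonal influenza vaccine within 14 days after study vaccination".

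The Table 8 shell has separate PP sections for each visit, with repeated "rows for Days 29, 91, 181, 273, 366". Its implementation note says: "Other exclusion criteria described in Section 6.3.4 will be added to the per protocol sections of this table when applicable". Its footnote for deviations reads: "Participant data are excluded from the per protocol analyses at all timepoints that occur at or after this protocol deviation". The same footnote ends by keeping whatever was collected before the exclusionary criterion was met.

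**The concern.** Two sections appear to disagree. In 8.1 the PP analysis is triggered by protocol deviations. In 6.3.4 the events that matter most for late titres are expressly not deviations, so on a literal reading they would not trigger it.

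The unit of exclusion is also open. If an infection at Day 300 removes the participant, that person's Day 15 and Day 29 results leave the PP set; if it removes observations, they stay. Two programmers could therefore produce different PP tables. N-antibody is planned only at Days 1, 91, 181, 273 and 366 (Table 48), so an infection known only from serology is dated to an interval. It is not said whether a positive result at Day 1 counts as breakthrough.

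Antibody magnitude at all timepoints is a co-primary endpoint. Without a companion analysis, a Day 273 or Day 366 geometric mean could be read as durability of the Ad26.COV2.S boost when part of it comes from later exposure.

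**Working it through.** **1. Does the SAP commit to PP output?** The later paragraphs of 8.1 say that interval estimates will be presented in Tables 13 to 28, 29 to 36 and 37 to 44. That is 44 − 13 + 1 = 32 tables. The even-numbered ones, 14 to 44, carry the PP title: (44 − 14)/2 + 1 = 16. Figures 2 to 65 pair mITT and PP in the same way. Section 6.3.4 says the PP population will be defined and the added criteria applied. The conditional sentence repeats Protocol 9.4.3 and is at odds with the rest of its own section; no listed output depends on it.

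**2. Is mITT wrongly built?** Protocol 9.3 requires a dose plus valid pre- and post-vaccination samples, and Protocol 9.4.3 presents immunogenicity on that set. The SAP follows both. It removes one later exposure, which is a study vaccine: data on Group 4E participants after they enter Group 15E are left out of Group 4E analyses (SAP 4.1).

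**3. The plan's own precision figure.** Interval factor = exp(t(0.975, n−1) × SD/√n). At n = 50 and SD 1.0 this is exp(2.0096/7.071) = 1.329. A GMT of 100 then gives 75.3 to 132.9, as in SAP Table 4.

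**4. What could post-event samples do to mITT?** The share f of samples taken after an event and the fold rise k are assumptions; the documents give neither. The GM inflates by k^f, and the SD becomes √(SD² + f(1−f)(ln k)²).

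| f, k | GM inflation | Interval factor, n = 50, SD 0.5 / 1.0 |
|---|---|---|
| 10%, 2 | 1.07 | 1.17 / 1.34 |
| 20%, 4 | 1.32 | 1.24 / 1.38 |
| 30%, 5 | 1.62 | 1.29 / 1.42 |

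The shift lies inside the interval in the first row, outside it only at SD 0.5 in the second, and outside at both SDs in the third. With n = 45, SD 1.0 and k = 4, simulation (20,000 samples per case) puts coverage of the event-free GM by the nominal 95% interval at 88%, 66% and 37% for f = 10%, 20% and 30%. A companion set is therefore worth having, and step 1 shows that it is planned.

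**5. What does the unstated unit change?** At Day 366 both readings drop everyone with an earlier event, so they coincide. They differ at visits before the event. Dropping whole participants takes an early visit from n = 50 to 50(1 − f). At SD 1.0 the factor goes from 1.33 to 1.35 (f = 10%, n = 45), 1.38 (20%, n = 40) or 1.41 (30%, n = 35). The early GM would also move by r^f, where r is the early titre ratio of those with later events to those without; r is unknown. For the influenza criterion the event falls within 14 days of the boost, so removal from the event onward takes out nearly the same post-boost visits as removal of the participant.

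**6. Which reading do the shells support?** Visit-specific PP sections in Table 8, an example in Listing 6 that excludes a participant from PP at a given day, and the last sentence of the deviation footnote all fit removal from the event onward with earlier visits kept. The implementation note puts the added criteria into those same sections.

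**7. Precision of the PP set.** At SD 1.0 with 40% removed: whole group n = 30, 1.45; age stratum n = 15, 1.74 (against 1.51 at n = 25); live-virus subset n = 12, 1.89 (against 1.60 at n = 20).

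**The case for a change.** The strongest case for a change is that a SAP should settle such choices before analysis. The deviation footnote is attached to the deviation row and is not extended to the added criteria, and the words in 6.3.4 allow either unit. That stands as missing detail: the shells point to a reading without stating it, and the status of a positive N-antibody result at Day 1 is open. A line in the programming specification settles both. Table 48 reports Day 1 positives and Table 49 counts reported infections, outside vaccines and participants with neither, so a reader can see how many people the choice touches.

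It can also be said that the immunogenicity reviews in SAP 6.6.2 name only mITT. That section does not say whether those reviews reach Day 91, and the abbreviated analysis plans mentioned in Protocol 9.4 are not among the documents, so nothing can be concluded there.

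Nor is the PP set a clean answer. It conditions on staying uninfected and without an outside vaccine, so it is itself selected, and it is less precise within age strata. That supports showing it beside mITT, as the table list does.

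**Conclusion.** No change to the plan is needed. The conditional sentence in 8.1 is a clerical carry-over from the protocol; bringing it into line would alter none of the 32 tables. Retaining post-event samples in mITT is the protocol's definition, with PP as the companion set. The unit for the three added criteria is a gap that the shells let analysts fill sensibly. On the participant-level reading, early-visit interval factors in a whole group would widen from 1.33 to at most 1.41 for event shares up to 30% (SD 1.0, starting from 50); late visits would barely differ. The study is descriptive and tests no hypothesis, so no decision rule turns on the choice. This rests on the PP tables being produced as listed. The inflation range of 1.07 to 1.62 rests on assumed event shares and fold rises.
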